### **6.3. DATA MONITORING PLAN**

#### **6.3.1. Monitoring for Side Effects and Adverse Events**

Any infant that develops side effects or minor adverse effects related to the intervention can be continued on study medication at the discretion of the attending physician but the event will be recorded for the trial. If the infant demonstrates tachycardia of 220 beats per minute for greater than 60 minutes, the clinical team should hold the study drug for 24 hours. If tachycardia resolves, the study drug may restart.

Enrolled infants will have their inpatient record reviewed by research coordinators to obtain the following data:

- Infant weight: at birth, day of randomization, and status
- Heart rate: Number of days after randomization until status that there were at least two consecutive heart rates documented over 200 bpm (when infant was not crying) at least 3 hours apart
- Treatment for high blood pressure initiated after randomization until status
- Gastrointestinal issues (NPO for more than 24 hours)
- Use of reflux medications at status

In the largest caffeine trial, the Caffeine for Apnea trial, initial decreased weight gain was reported in the caffeine group as compared to the placebo group but with continued caffeine treatment, long-term weight gain did not differ between caffeine and placebo group infants. Differences in weight gain from the day of randomization, day of discharge (status), and at the infant's well child visits (e.g. one and/or four week periods discharge) will be monitored

Apnea/bradycardia:

The trial will allow for individual study sites to continue their standard practice, and the definition of AoP will be left at the discretion of the neonatology staff treating the infant. If an infant develops apnea, treatment will be left at the discretion of the attending neonatologist or institution. The etiology of the ensuing event and its management (e.g. CPAP, mechanical ventilation, sepsis) will be recorded. Apnea and bradycardia are common in eligible infants even with caffeine treatment and will not be considered serious adverse events.

Other complications of prematurity that are not likely to be related to the intervention will also be collected following randomization into this trial. These include development of necrotizing enterocolitis, intraventricular hemorrhage, periventricular leukomalacia, late onset sepsis, and severe retinopathy of prematurity.

In addition, the following data will be obtained from the family during follow-up calls and from returned mailed-in forms:

- Infant weights at all health care provider visits (well child and sick visits)
- Reasons for sick visits to the Health Care Provider, urgent care, or emergency room
- Reasons for admission to the hospital
- Final diagnosis when discharged from the hospital

A member of the research staff will be available during the day (8 am to 5 pm) for questions regarding the study medication and trial. If the infant requires medical attention, it should be addressed by the Health Care Provider or emergency medical care staff. The evaluating physician should treat the patient's medical needs, regardless of the involvement in the trial. Once the patient is stable, if the physician or parent/guardian requires further information related to the trial, a member of the research team may be contacted. Information obtained from the trial is unlikely to change the immediate care of the patient if sick.

Expedited serious adverse events will be reported per local IRB guidelines, and to the NICHD and NRN Data Coordinating Center at RTI.

The trial will record side effects and any study related serious adverse events will be reported to the DSMC periodically. Expedited serious adverse events will be reported per local IRB guidelines, and to the NICHD and the NRN Data Coordinating Center at RTI. All protocol deviations and violations will be reported.

The following detail describes the action to be taken for each adverse event below:

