- a. The administration of study medication at home by the parents without frequent missed doses
- b. Loss to follow up
- c. Inaccurate or missing information regarding re-admission to the hospital or to sick visits
- d. Inaccurate data collection on follow-up forms provided by the parents
- e. Side effects from the study medication

The trial will be approved by each institutional review board (IRB). Parental consent will be obtained for each infant enrolled. Safety is of upmost importance and will be monitored by the Data Safety Monitoring Committee (DSMC) when 25%, 50%, and 75% of the subjects complete the eight-week follow up period (or are lost to follow up). The trial will record side effects and adverse events will be reported to the DSMC periodically. Expedited serious adverse events will be reported per local IRB guidelines and to the NICHD and NRN Data Coordinating Center at RTI.

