### **Arrhythmias and seizures**

Both arrhythmias (excluding those due to tachycardia or bradycardia) and seizures will be considered serious adverse events. Seizures have been reported with overdoses of caffeine (multiple doses of 20 mg/kg or more) and therefore would be unexpected. However, should seizures occur in the hospital, it will be evaluated and managed by individual study site policies or attending neonatologist. Infants whose medication is held or stopped based on decision made by the attending neonatologist will be included in the analysis as the design includes intention to treat analysis. Episodes of arrhythmia (excluding those due to tachycardia or bradycardia), seizure, and other unexpected, related serious adverse events will be documented for the results of the trial, and the outcome is to be reported to the NICHD and RTI.

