### **Hospitalization, sick visit to urgent care, emergency room or health care provider's office related to apneic or apparent life-threatening event (ALTE)**

Hospitalization, sick visit to urgent care, emergency room or health care provider's office related to apneic or apparent life-threatening event (ALTE) will be considered serious adverse events. Readmissions to the hospital and sick visits to urgent care, emergency rooms, or health care provider's office related to apneic or apparent life-threatening event (ALTE) within the first eight weeks after discharge from the hospital will be collected for the results of the trial, and the outcome is to be reported to the NICHD and RTI

Infants will be monitored prospectively while in the NICU. Interim efficacy and safety will be formally evaluated by the independent Data Safety Monitoring Committee as specified in detail in Section 6.3.3.2.

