## 10.4 Deaths and Serious Adverse Events

A serious adverse event (SAE) is any event that is life threatening, results in death, causes or prolongs hospitalization, leads to a disability or birth defect, or requires an intervention to prevent a disability. SAEs will be listed, and SAEs and treatment-related SAEs will be summarized in the manner mentioned in Section 10.3 if there are enough events to summarize. Deaths will be listed.

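### Serious adverse events outside the listed outcomes are assured of recording and DSMC review only if judged related, which conflicts with Protocol 3.4 and SAP 10.4

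*Protocol*

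**What the plan says.** Four statements bear on which SAEs are recorded, monitored and tabulated.

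- **DSMC reporting, Protocol 6.3.1, with the same sentence in SAP 7.4 (Additional Data Monitoring):** "The trial will record side effects and any study related serious adverse events will be reported to the DSMC periodically".
- **Recording, Protocol 6.3.1, Arrhythmias and seizures:** besides arrhythmia, the text covers "seizure, and other unexpected, related serious adverse events will be documented for the results of the trial".
- **DSMC reporting, Protocol 3.4:** "The trial will record side effects and adverse events will be reported to the DSMC periodically". No relatedness condition is attached.
- **Final tables, SAP 10.3 and 10.4:** an SAE is defined by seriousness alone (for example, life threatening, or causing or prolonging hospitalization). "SAEs will be listed, and SAEs and treatment-related SAEs will be summarized in the manner mentioned in Section 10.3", provided there are enough events. SAP 10.3 collects specific adverse events on a log and tabulates them by severity and by relationship to treatment.

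Some events are serious by rule, with no judgement about study drug. The Protocol states "Both arrhythmias (excluding those due to tachycardia or bradycardia) and seizures will be considered serious adverse events", and hospitalizations and sick visits "related to apneic or apparent life-threatening event (ALTE) will be considered serious adverse events". SAP section 13 declares no changes from the protocol analyses, so the differences above are not acknowledged.

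**The concern.** The protocol's safety hypothesis (3.1.2 d) is that there will be no increase in side effects or adverse events; it is not confined to related ones. Protocol 3.4 says that no data exist on the safety of late-hospital and home methylxanthine treatment, so the trial should be able to pick up a harm nobody named in advance.

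Judging causality event by event is a weak tool for that. Protocol 4.5.2 lists many complications that these infants face from prematurity anyway, and a single event is easily put down to them. Comparing counts between randomized arms needs no such judgement. A relatedness condition applied before recording or forwarding gives up that comparison for the events it screens out.

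**Working it through.** No figure in the plan decides this point. The one number attached to interim safety monitoring is the Pocock bound, p < 0.0158. It reproduces for 5 equally spaced looks at overall two-sided 0.05 (constant 2.4132, nominal p = 0.0158). It applies to AoP-related visits, ALTE episodes and hospitalizations, and does not change with the SAE filter. The check is therefore to follow event types through the text.

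**Step 1. Trace four kinds of event, each assumed to be judged unrelated.**

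1. *Treated seizure or arrhythmia in hospital.* SAE by rule, and a safety outcome in Protocol 4.2. DSMC reports show safety outcomes by group (Protocol 6.3.3). Not lost.
2. *Necrotizing enterocolitis, intraventricular hemorrhage, periventricular leukomalacia, late-onset sepsis or severe retinopathy.* Protocol 6.3.1 collects these although it regards them as unlikely to be related. Interim Safety Monitoring examines the 6.3.1 outcomes by group. Not lost.
3. *Readmission or sick visit for any cause after discharge.* Counted as a secondary outcome, reported to the DSMC by group, with reasons collected (Protocol 4.2, 6.3.1, 6.3.3). Not lost.
4. *An unlisted, non-fatal in-hospital event that is life threatening or prolongs the stay.* It meets the SAP 10.4 definition. The Arrhythmias and seizures paragraph does not provide for recording it, and the 6.3.1 and SAP 7.4 sentence does not send it to the DSMC. Under Protocol 3.4 it would be sent. Any added hospital days enter the primary outcome in aggregate, without the type of event.

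Death is an outcome and is reported by group, so it behaves like cases 1 to 3.

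**Step 2. Set the rules against each other for case 4.** On DSMC reporting, Protocol 3.4 says yes; Protocol 6.3.1 and SAP 7.4 provide for it only if related. On recording, SAP 10.4 needs all SAEs, while the Protocol provides for unlisted ones only if unexpected and related. SAP 10.3 does not close the gap because its log is limited to specific adverse events.

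**Step 3. Illustration with assumed rates, at the final minimum sample of 439 per arm only.** Power ≈ Φ(|p1 − p2| / SE − 1.96), with SE = √{[p1(1 − p1) + p2(1 − p2)] / 439}, two-sided 0.05.

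- All events reported, 8% vs 4%: SE = √(0.1120 / 439) = 0.01597; 0.04 / 0.01597 − 1.96 = 0.544; power 71%.
- Half judged related in both arms, 4% vs 2%: SE = √(0.0580 / 439) = 0.01149; 0.02 / 0.01149 − 1.96 = −0.220; power 41%.
- A quarter or a tenth judged related: 23% and 12%.
- At 6% vs 3%: 58% with full reporting, then 32%, 18% and 10%.
- At 2% vs 1%: 23% even with full reporting.

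No document supports these rates or fractions, and no DSMC test of these events is planned. The figures also do not describe visibility at interim looks. With equal arms and full reporting, 8% vs 4% gives 13% power at 100 infants, 31% at 300 and 54% at 600.

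**The case against.** The strongest reply is that the safety net is much wider than the quoted sentence suggests. Most serious events likely in this population are serious by rule, listed as outcomes, or counted as readmissions or visits, and all of these reach the DSMC by group without a relatedness judgement. That stands, and it confines the point to case 4.

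Three stronger readings are tempting, and the documents do not support them.

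- *Only related SAEs are recorded or seen by the DSMC.* Cases 1 to 3 and deaths show otherwise.
- *The all-SAE table cannot be produced.* It can be, from the events collected. SAP 10.3 tabulates by relationship, which presupposes that some unrelated events are recorded, and the SAP 10.4 summary is conditional on enough events. The table may be incomplete; it is not impossible.
- *Masked site clinicians decide what is forwarded.* SAP 4.6 says site staff are masked, but neither document says who assigns relatedness.

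The reply might add that the Adverse Events Form could capture everything. The form is named in Protocol section 9 but its content is not shown, so this cannot be relied on or ruled out.

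**Conclusion.** The point holds for SAEs outside the listed outcomes, mainly unlisted, non-fatal, in-hospital events. For these, the plan assures recording and DSMC review only after a judgement of relatedness. That contradicts Protocol 3.4 and falls short of what SAP 10.4 intends to tabulate. An arm imbalance in this category could be missed during the trial, and the final all-SAE summary may depend partly on attribution.

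The size is unknown because no document gives a rate for these events. The power figures above show direction only: they assume the event rates, assume equal attribution fractions in both arms, and apply at the final minimum sample. They should not be read as the loss in interim monitoring. The gap is real and cheap to close, with substantial safeguards around it; the sponsor should correct it, but it does not undermine the trial's safety monitoring as a whole.

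**What to change.** - **Protocol 6.3.1 and SAP 7.4 (Additional Data Monitoring):** in the sentence on periodic DSMC reporting, replace the study-related wording with *all serious adverse events, by randomized group (A/B) and regardless of judged relationship*. Align the sentence in Protocol 3.4.
- **Protocol 6.3.1, Arrhythmias and seizures:** delete the qualifiers *unexpected* and *related*.
- **Both documents:** use the SAP 10.4 definition of an SAE, keeping the Protocol 6.3.1 exception under which in-hospital apnea and bradycardia are not SAEs.
- **SAP 10.3:** state that the log captures all SAEs as well as the specified adverse events. Without this, the other edits leave the log narrower than the table.
- **Relatedness:** keep it as a recorded attribute, and name who assigns it.

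The cost is somewhat more SAE recording and longer DSMC listings. It is more than a wording change in one respect: these infants are already inpatients, so sites will need a collection rule for when an event counts as prolonging hospitalization. Whether the Adverse Events Form needs new fields cannot be told from the documents. If events have already been collected under the narrower rule, SAP 10.4 should say that its all-SAE summary is limited to them.

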### **Arrhythmias and seizures**

Both arrhythmias (excluding those due to tachycardia or bradycardia) and seizures will be considered serious adverse events. Seizures have been reported with overdoses of caffeine (multiple doses of 20 mg/kg or more) and therefore would be unexpected. However, should seizures occur in the hospital, it will be evaluated and managed by individual study site policies or attending neonatologist. Infants whose medication is held or stopped based on decision made by the attending neonatologist will be included in the analysis as the design includes intention to treat analysis. Episodes of arrhythmia (excluding those due to tachycardia or bradycardia), seizure, and other unexpected, related serious adverse events will be documented for the results of the trial, and the outcome is to be reported to the NICHD and RTI.

### **Hospitalization, sick visit to urgent care, emergency room or health care provider's office related to apneic or apparent life-threatening event (ALTE)**

Hospitalization, sick visit to urgent care, emergency room or health care provider's office related to apneic or apparent life-threatening event (ALTE) will be considered serious adverse events. Readmissions to the hospital and sick visits to urgent care, emergency rooms, or health care provider's office related to apneic or apparent life-threatening event (ALTE) within the first eight weeks after discharge from the hospital will be collected for the results of the trial, and the outcome is to be reported to the NICHD and RTI

Infants will be monitored prospectively while in the NICU. Interim efficacy and safety will be formally evaluated by the independent Data Safety Monitoring Committee as specified in detail in Section 6.3.3.2.

### **6.3.2. Monitoring Drug Adherence and Compliance**

Adherence to medication regimens is affected in a multi-factorial manner. A review of 51 studies with 19 chronic diseases found a wide range of factors for lack of compliance, falling within categories of socioeconomic, patient-related, and therapy-related determinants. The conclusion of this large systematic review points to the use of multiple methods to better attain compliance with medications at home.

For this trial, we will combine two recommended methods to assure adequate monitoring and improve compliance with medication administration:

- a. While the infant remains inpatient, the medication will be administered by the nurse as directed and the research nurse will perform a chart review at least twice a week to ensure study medication is being received after randomization and prior to discharge.
- b. After discharge:
  - i. A Medication form will be supplied to the parents. This will include a daily item to mark if medication was administered. In addition, parents can use this form to record sick visits to the Health Care Provider, emergency room, or hospitalizations as well as weights obtained during well-child or sick visits and missed doses of study medication. Any new medications prescribed will also be noted on this form.
  - ii. A Follow-up form will be supplied. This will be similar to the Medication form, but will be used during the second four-week period discharge and will not include a medication administration section. Safety outcomes (such as Health Care Provider, Emergency visits, and re-admissions to a hospital) will be recorded on this form also.
  - iii. A member of the research team will contact the parents within the first 72 hours after discharge to answer questions and assess medication compliance.
  - iv. A member of the research team will contact the parents once a week during the first 4 weeks and biweekly during weeks 5-8 to address concerns and evaluate medication compliance\*. During this contact, the parents will be asked about any well or sick visits made to the health care provider, urgent care, emergency room, or hospital since the last contact and the reason for these visits.

\*To assure both safety and compliance, vials will be marked with a number corresponding to the beginning day of medication to be administered at home. For example, the next day after discharge, the parent is to administer the study drug from the vial marked #1 by oral syringe. The following day, the vial marked #2 should be given. This procedure, using an oral syringe, should be followed until day 28 after discharge when the last medication vial marked #28 should be

given. If a dose is missed, it may be given at any time on that day as long as it is given at least 12 hours before the next dose is due the next day. If it was not given at all, the parents will be instructed to discard the dose that was missed and record it on the medication form. The schedule of medication administration will then continue with the next numbered vial. This information will be noted for further analysis at the conclusion of the trial. Because of the long half-life of caffeine, single missed doses will have little clinical effect.

### **6.3.3. Statistical Interim Monitoring and Stopping Rules**

Statistical interim monitoring for this trial will be conducted by the independent Data Safety and Monitoring Committee using data and analyses provided by the NRN Data Coordinating Center at RTI. We recommend that the Data Safety and Monitoring Committee meet formally to review interim safety, efficacy and futility, as well as other aspects of accruing data (such as enrollment, data completeness and protocol compliance) four times during the study, after 100 infants complete the eight-week follow up and then roughly after 25%, 50% and 75% of subjects complete the eight week follow up. Formal Data Safety and Monitoring Committee reports will be prepared by the Data Coordinating Center for these meetings. These reports will include the following information:

- Brief summary of the trial design, including primary and secondary hypotheses and outcomes, study population, inclusion and exclusion criteria, recruitment, screening, randomization and study intervention procedures, and statistical considerations for trial design and analysis
- Interim monitoring plan
- Enrollment, including screening, consent, randomization and study exit
- Completeness of data and edit queries. Baseline study population characteristics, overall and by treatment group
- Drug adherence and compliance
- Primary efficacy outcomes by treatment group
- Secondary efficacy outcomes by treatment group
- Safety outcomes, including death, by treatment group
- Protocol deviations and violations, overall and by treatment group.

These Data Safety and Monitoring Committee reports will be blinded, with treatments labeled as group A and group B. As per the NRN Data Safety and Monitoring Committee Charter, the DSMC may, however, request to be un-blinded to perform their duties. If the Data Safety and Monitoring Committee recommends modification or cessation of the study protocol due to safety concerns, NIH will make the final determination.

#### Interim Safety Monitoring

Statistical interim safety monitoring will be conducted by the DCC after 100 infants complete the eight-week follow up and then after 25% (300), 50% (600), and 75% (900) of the infants enrolled complete the eight-week follow up period. Formal safety assessment will be based on the number of sick visits, emergency room visits, apparent life-threatening event episodes or hospitalizations related to AoP. Relatively liberal Pocock safety bounds based on 5 interim safety looks at the data will be constructed to guard against any occurrence of false positives while at

the same time allowing for stopping at reasonable levels of evidence. Thus, at each of these safety looks, an increased incidence of the above safety events in the Caffeine group with  $p < 0.0158$  will be considered as statistically significant evidence of harm that the Data Safety and Monitoring Committee can use to recommend suspension of the trial for safety reasons. In addition to the formal safety outcome, other safety outcomes collected in this trial (see section 6.3.1) will also be examined by treatment group. If a death occurs in either of the groups, the Data Safety and Monitoring Committee will review the cause of death and determine if the cause is linked to the study intervention. If it is deemed to be related to the intervention as an increased risk, the Data Safety and Monitoring Committee may recommend stopping the trial. After the Data Coordinating Center conducts each of these interim safety analyses, it will inform the Chair of the Data Safety and Monitoring Committee (or her designee) if there is any suggestion of a trend in the safety data. The Data Safety and Monitoring Committee Chair will then determine any future course of action, including convening a meeting of the entire panel to discuss the safety data.

